All drugs to be used are pre-qualified by WHO, MSF and licensed for use in India by Indian regulatory authorities. In case of generics, only drugs from MSF-prequalified manufacturers will be used. MSF's qualification of pharmaceutical products follows WHO norms. Procurement of the drugs will follow the MSF standard, in accordance with the national regulations. All products will be stored in a secured area, under storage conditions recommended by the manufacturer and in accordance with applicable regulatory requirements. Following are manufacturer details of drugs to be used for the study

Safety assessment

The study will collect and report on standardized forms Adverse Events (AE) and Adverse Reactions (AR) leading to death, modification or discontinuation of treatment (See CRF AE and Appendix 4). As recommended, tolerance and monitoring for adverse events associated with the use of the proposed regimen will be searched for at each visit through clinical and laboratory examination (i.e. alanine transaminase, creatinine, haemoglobin). Monitoring of adverse events will follow the manufacturer recommendation. Treatment will be adjusted according to the recommendations of the manufacturers and of the national and international institutions or MSF medical guideline. The study team will notify immediately and within 48 hours all AE that led to treatment modification, to the study site principal investigators through a specific form (CRF AE, Appendix 4). In case of serious adverse event or reaction, the study principal investigators will be informed within 48 hours and then inform within seven days to the study Scientific Committee and the local Ethical Review Board. In the event of a serious adverse event occurring, the Indian national "Suspected Adverse Drug Reaction Reporting Form" will be completed. This can be found at the following web link:

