<http://www.ipc.gov.in/PvPI/ADRReportingForm.pdf>. All AE or AR considered as serious AE or leading to a change in the treatment, from the date the patient starts the HCV treatment, during the entire treatment follow-up, and up to four weeks after the intake of the last regimen drug should be reported. In addition, serious AE that occur after this period and during the post-treatment follow-up should be reported if the event is suspected to be related to any of the drugs included in the regimen. The decision to postpone, modify or to interrupt/discontinue the regimen will be left at the discretion of the clinical team following discussion with the study principal investigators and with the medical HCV referent of the

section. For all AEs, patients will receive the best care available and will be followed up until resolution.

List of potential adverse events and their management are provided in appendix 6

Medical advisory panel

The study is supported by a medical co-ordinator, study principal investigator, based in the Delhi Co-ordination of MSF. Regular program committees will be held to discuss medical or program issues. The program committee also has a access to a team of experts, including clinicians and virologists specialized on HCV treatment, who will advise on the individual patient management and treatment decisions in case of specific conditions. The program committee and the experts will have access to coded clinical and biological data collected during the study, as appropriate, from patients requiring specialized care.

Standardized documents with the required information will be used. The review and patient decision will also involve closely the MSF medical team and medical coordinator in each study site. Recommendations will be based on patient's records data, on current international and national recommendations and on the availability of access to drugs in the country.

VIII. Study Outcome Measures

The primary endpoint is the proportion of patients with sustainable viral response at 12 weeks, among patients who initiated HCV treatment (irrespective of regimen).

The endpoint will be plasma HCV-RNA response at week 12 after end of treatment (EoT). Treatment success is defined as viral load as either undetectable or below a concentration of 12UI/mL Treatment failure is defined as either a detectable viral load 12 weeks after cessation of treatment, death or loss to follow-up, medical decision to exit the study or transfer-out.

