- Frequency and type of demographic, clinical and biological risk factors associated with treatment outcomes: age , sex, liver fibrosis stage, child pugh score, genotype, clinical symptoms, comorbidities with HBV infection , addiction
- Concerning the safety of HCV treatment: Frequency and type of treatment-related side effects or events that cause modification of dosage of the HCV treatment
- Frequency and type of treatment-related side effects that cause permanent interruption (discontinuation) of the HCV treatment
- Concerning the feasibility of HCV treatment: Proportion of patients included in the cohort but non eligible to treatment at the first assessment, by clinical and biological characteristics, over time (yearly eligibility assessment): HCV viral load, liver fibrosis stage, child pugh score, presence of ascites,HIV viral load
- Frequency and type of demographic, clinical and biological risk factors associated with non-eligibility to treatment: age , sex, fibrosis stage, child pugh score, genotype, clinical symptoms, biological anomalies, comorbidities with HBV infection, addiction
- Frequency of reporting of missed doses by patients

IX. Data management

Data Collection Tools

Paper based questionnaires and lab forms will be used for collection of individual baseline information, clinical evaluation information, laboratory results and treatment information. The different CRFs are presented in Appendix 1 and 2. Other data collection tools may be used in the laboratory. Questionnaires will be pre-tested prior to initiation of data collection. Study forms will be linked through unique study numbers assigned to study participants. Personal identifier information will be recorded on separate forms, and will be kept separately to maintain confidentiality.

Listing of data collection questionnaire (Appendix 1 & 2):

- Baseline information
- Consultation form
- Comorbidities form
- Biological form

- Adverse Events form

In case of adverse events, specific reports will be filled, initial and follow up reports (Appendix 3).

Prior to the inclusion in this cohort, the patient may be under medical follow up for his HIV and / or HCV care. These data are collected on different tools. Some information would be used for this study. As example, the CD4 count at enrolment will be found in the HIV database used in the HIV care facility. The source of the data is specific to each site. The data will be reported to the HCV database.

Data Management and Monitoring

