 Adverse event/pregnancy leading to Modification	 or Discontinuation of treatment(+ fill CRF AE)
 Stop for other reasons (skip to 280)	 Treatment Finished (skip to 280)
273_ If under HCV treatment: How many doses have been missed for the last three days? _____  DK (dose = all pills taken at the same moment during the day)	
274_ Treatment if initiation or modification (do not fill if continuation of same regimen)	
Drug _____	Dosage _____ mg per day / per week
Drug _____	Dosage _____ mg per day / per week
Drug _____	Dosage _____ mg per day / per week

280_ End of follow up:	 Yes  No	if Yes, skip to question 290
281_ Date of the next consultation (for HCV care) ____ - ____ - ____ (dd-mm-yyyy) (go to next page)		
290_ Reasons of End of Follow up in HCV care (end of questionnaire)		
 Cured	 Transfer out	 Medical decision to stop HCV Follow up
 Death	 Loss of Follow up	

To be filled by the COUNSELLOR

Pt file N° _____	Data clerk Initials: _____
Visit N°: _____	Date data entry: ____ - ____ - ____ (dd-mm-yyyy)
Name of interviewer: _____	

COUNSELLOR:	Addiction Follow-up		
230_ Drug use since last visit	 Yes	 No	 DK
231_ Opioid substitution program (or OST)	 Yes	 No	 DK
232_ Alcohol use since last visit	 Yes	 No	 DK

COUNSELLING SESSION (Information entered in Hepa-MUD)			
300_ Counselling Focus (only one answer is possible, mark ONLY the main focus of the session)			
 Enhanced Coping			
 Enhanced Motivation			
 Practical Support			
 Family related issues			
 Adherence issues			
 Alcohol use			
 Lifestyle changes			
 Drug Use / Harm reduction			
 Mild/moderate depression			
 Other Mental Health issues			
 Regular follow-up			

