Appendix 4: Adverse Events Reporting Form

CRF AE_ N° Visit: _____

1_Surname: _____	2_Forename: _____	(not to enter in the database)
Patient's file N° _____		
3_ Identification cohort Number: _____ 4_ ID Key _____		

10_Date of consultation: ____ / ____ / ____ (dd/mm/yyyy)	12_Name of interviewer: _____	14_Data clerk initials: _____
11_Site of consultation: _____	13_Doctor / Clinical Officer / Nurse / Others	15_Date of data entry: ____ / ____ / ____ (dd/mm/yyyy)

Instructions: Only for the events leading to a change in the HCV treatment: change of drugs, change of dosage or interruption of treatment.
Fill all the questions. If the answer is unknown, tick the box DK (don't know)

Neurologic / Psychiatric			
501_Depression	 Yes	 No	 DK
502_Mania	 Yes	 No	 DK
503_Headache	 Yes	 No	 DK

Ocular / visual / hearing (from baseline)			
504_Eye disorders	 Yes	 No	 DK
505_Hearing Loss	 Yes	 No	 DK

Gastrointestinal			
506_Increase jaundice- hepatitis flare	 Yes	 No	 DK
507_Diarrhea	 Yes	 No	 DK
508_Nausea/ vomiting	 Yes	 No	 DK

Skin – Dermatological			
509_Rash	 Yes	 No	 DK
510_Photosensitivity	 Yes	 No	 DK
511_Hair loss	 Yes	 No	 DK

Musculoskeletal/ respiratory			
512_Cough/Respiratory Tract symptoms	 Yes	 No	 DK
513_Arthralgia/myalgia	 Yes	 No	 DK
514_Cardiologic problem	 Yes	 No	 DK

Endocrine / metabolic			
515_Diabetes Mellitus	 Yes	 No	 DK

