516_Thyroid dysfunction	 Yes	 No	 DK

Biology anomaly			
517_Anemia	 Yes	 No	 DK
518_Neutropenia	 Yes	 No	 DK
519_Thrombocytopenia	 Yes	 No	 DK
520_Increase of ALT/AST	 Yes	 No	 DK

521_Other: specify _____

522_Pregnancy Yes No DK *If yes, fill the specific report form*

523_Is the Adverse event is considered as **Serious Adverse Event**: Yes No DK
If yes, fill the specific report form

Signature of the clinician _____

Transfer to Site Investigator (PI) Yes No DK

Date received by study PI ____ / ____ / ____ **Signature study PI** _____

Appendix 6

Management of the adverse effects

The main side effects associated with sofosbuvir are:
Sofosbuvir+ ribavirin - fatigue, headache, anaemia

Table 1. Treatment –emergent adverse events (all grades) reported in (> or = 15% of subjects in any treatment arm (Source Sovaldi package insert p.6)

Symptom	Interferon free regimen		
	Placebo 12 weeks N=71	SOF+RBV 12 weeks N=650	SOF+RBV 24 weeks N=250
Fatigue	24%	38%	30%
Headache	20%	24%	30%
Nausea	18%	22%	13%
Insomnia	4%	15%	16%
Pruritus	8%	11%	27%
Anemia	0%	10%	6%
Asthenia	3%	6%	21%
Rash	8%	8%	9%
Decreased appetite	10%	6%	6%
Chills	1%	2%	2%
Influenza Like Illness	3%	3%	6%
Pyrexia	0%	4%	4%
Diarrhea	6%	9%	12%
Neutropenia	0%	<1%	<1%
Myalgia	0%	6%	9%
Irritability	1%	10%	10%

Table 2: Management of adverse effects

Side effect	Comments	Suggested Management Strategies
GENERAL		
Fatigue	Fatigue is very common in patients with HCV and is probably increased on treatment with ribavirin. The following are not helpful in management of fatigue: dose reduction,	
 1. Check haemoglobin 2. Screen for depression 3. Suggest behavioural strategies to conserve energy e.g. rest periods, napping, planning ahead 4. Adequate fluid intake
Injection site reaction	Redness and induration are common. Occasionally painful nodules or ulceration may develop	
 1. Review technique for injection 2. Avoid painful or ulcerated areas

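### Safety endpoints rest on treatment-relatedness, which neither printed case report form records, so non-serious events can only be counted for all causes

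*Protocol*

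**What the plan says.** Section 6.VIII lists two safety endpoints. One is "Frequency and type of treatment-related side effects or events that cause modification of dosage of the HCV treatment". The other is "Frequency and type of treatment-related side effects that cause permanent interruption (discontinuation) of the HCV treatment".

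The Safety assessment part of section 6.VII says the study will collect "Adverse Events (AE) and Adverse Reactions (AR) leading to death, modification or discontinuation of treatment", so it treats events and reactions as different things. Serious or treatment-changing events are reportable from the start of treatment "up to four weeks after the intake of the last regimen drug should be reported". Later serious events "should be reported if the event is suspected to be related to any of the drugs included in the regimen".

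CRF AE in Appendix 4 opens with "Instructions: Only for the events leading to a change in the HCV treatment: change of drugs, change of dosage or interruption of treatment". It then holds identifiers, a consultation date, a data-entry date, a Yes/No/DK list of event types (items 501 to 520), other (521), pregnancy (522), seriousness (523) and sign-off. CRF2 item 272 in Appendix 2 offers "Adverse event/pregnancy leading to Modification" as one box and discontinuation as the next, with an instruction to complete CRF AE.

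Section 6.IX promises initial and follow-up adverse-event reports and places them in Appendix 3.

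**The concern.** The discontinuation endpoint is limited to treatment-related effects. On one reading the modification endpoint is too, although its wording can also take in events of any cause. Relatedness is a judgement made by the treating clinician. If the form never asks for it, an analyst must either count every recorded event as drug-related or assign cause afterwards without a recorded opinion. Neither gives the endpoint as defined. A later statistical analysis plan cannot repair this, because it cannot analyse a judgement that was not recorded.

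Safety and tolerance are secondary objectives d, e and f in section 4. All patients who start are treated, with no untreated or placebo arm against which background illness could be subtracted. Counting every event as drug-related would therefore push apparent toxicity upward only.

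Two lesser gaps lie beside this one. The discontinuation endpoint requires the stop to be permanent, and section 6.VII recognises interruption as well as discontinuation. The reporting rule also changes four weeks after the last drug intake, which makes the timing of an event matter.

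**Working it through.** The protocol states no figure on this point, so there is none to reproduce. The check compares what the endpoints and the reporting rule need with what each printed form holds.

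| Needed | CRF AE (Appendix 4) | CRF2 (Appendix 2) | Result |
|---|---|---|---|
| Relatedness to the HCV drugs | No item | No coded item; a free-text consultation space only | Not recorded as data for non-serious events |
| Modification or discontinuation | No item; one form covers drug change, dose change and interruption | Item 272 has a separate box for each; item 274 gives the drugs and dosage after a change | Can be derived |
| Permanent or temporary stop | No item | No box for a temporary stop caused by an adverse event | Must be inferred from item 272 and later visits |
| Onset date | Consultation date only | Consultation date only | Late proxy |
| Pregnancy separate from adverse event | Item 522 | Pooled in item 272 | Can be derived by joining the forms |
| Seriousness | Item 523 | No item | Recorded; details go to a form not reproduced |

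1. **Relatedness.** Let A be the number of patients whose treatment is stopped because of an adverse event, and R the number among them whose event the clinician would call related. Item 272 with CRF AE yields A. The endpoint asks for R. Reporting A in place of R overstates by A − R, a share of (A − R)/A. The protocol gives neither A nor R, so that share could lie anywhere from 0% (every event related) to 100% (none related).

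2. **Permanence.** A temporary hold has to be entered under one of the existing choices in item 272. It can be recognised later if a subsequent dated CRF2 shows treatment resumed. If the patient is lost after the hold, no later visit exists and the forms cannot say whether the stop was meant to be permanent. The protocol states no rule for this case.

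3. **Onset date.** An event that causes a dose change or a stop must begin before that change, so the four-week boundary does not enter either endpoint. It governs what must be reported after treatment, and beyond four weeks only serious, suspected-related events are reportable.

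4. **Cross-reference.** Appendix 3 is the laboratory results form and the laboratory schedule. The printed adverse-event form is in Appendix 4. The initial and follow-up reports named in section 6.IX are not at the place cited.

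**The case against.** The strongest reply is that the safety endpoints are largely recoverable, and much of it stands. A reader might infer from CRF AE alone that the endpoints cannot be derived at all. That goes too far: item 272 separates modification from discontinuation and links to CRF AE, item 522 separates pregnancy, and a restart would normally show at a later visit. The modification endpoint, read as covering events of any cause, may not need relatedness.

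A reader might also infer that the four-week reporting rule cannot be applied or audited. The documents do not support this. Serious events go to a specific report form and to the national suspected-reaction form; neither is reproduced, and either may hold onset and causality. Nor is a 12-week recording delay established. Table 3.0 lists no visit between the end of treatment and 12 weeks later, but it is a minimum schedule, HCV visits are integrated with HIV visits, and patients are told to return at any time if problems arise.

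It is tempting to size the overstatement from Appendix 6 Table 1, where fatigue is 24% on placebo and 38% on 12-week sofosbuvir plus ribavirin. The method fails on the same table. Anaemia is 0% against 10%, which would make every case drug-related. Decreased appetite is 10% against 6%, and 10/6 = 167% is impossible as a proportion. The table also counts events of all grades, not those that change treatment, and covers only one of the regimens in use.

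Finally, the protocol says the study is not a pharmacovigilance study, and clinicians discuss treatment changes with the investigators and the HCV referent. The judgement may well be made. It still has no field on the printed forms, and the endpoint is worded in terms of it.

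**Conclusion.** The point holds as a gap in data capture for secondary safety endpoints. For non-serious events, the discontinuation endpoint as worded cannot be produced from the printed CRF AE and CRF2, because relatedness is not recorded. All-cause counts can be produced. The missing onset date and the lack of an explicit temporary-interruption item are lesser weaknesses: the first does not affect the two endpoints, and the second leaves permanence to an unstated inference.

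The direction of the error, if all-cause counts are labelled treatment-related, is toward overstated toxicity. Its size cannot be estimated from the protocol. The conclusion assumes that the printed forms are complete and that the unreproduced reports are used only for serious events and pregnancy. If the initial and follow-up reports in section 6.IX cover non-serious events and include causality, the gap closes and only the cross-reference needs correcting. The primary endpoint is not affected. The change should be made, but the study does not depend on it.

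**What to change.** - Add three items to CRF AE: relatedness to the HCV drugs (related / not related / DK), onset date, and action taken (dose change / temporary interruption / permanent discontinuation).
- State how permanence is decided from the action-taken item and later CRF2 visits, including for a patient lost after an interruption.
- Make all-cause modifications and discontinuations driven by adverse events the main safety summary, with treatment-related events as a subset, and reword the two endpoints in section 6.VIII to match.
- Correct the section 6.IX reference to Appendix 3, and say where the initial and follow-up reports are and which events they cover.

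The cost is three form and database fields, completed only when CRF AE is filled, plus small wording changes. No treatment rule changes. For events already recorded without these items, report all-cause counts only, unless relatedness can be documented from contemporaneous notes.

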Demographic and baseline characteristics of the patients will be described using summary statistics (mean with their 95% CI or median with inter-quantile intervals for continuous data; frequency and proportion for categorical data). It will include (but not be restricted to): - age - sex – treatment received - clinical signs at inclusion, haemoglobin and other biological measures at inclusion.

Depending of the distribution of the data, different tests and reports of results will be provided. Distributions of categorical variables between two groups will be compared with the Fisher's exact test or chi-squared. Comparisons of continuous variables will be performed with a 2-sample t-test when the variable shows a normal distribution; otherwise, a Wilcoxon rank sum test will be performed.

Risk factors associated with the different outcomes will be assessed using univariate and multivariate models. Epidemiological and clinical relevant variables will be included in the multivariate model to obtain an adjusted measure of association.

To assess the APRI performance, compared to Fibroscan®, for assessment of liver fibrosis among HIV/HCV coinfecting individuals, sensitivity, specificity, negative predictive value, positive predictive value will be computed, across liver fibrosis scores.

We will use an alpha level of 5% for all statistical tests. All statistical tests will be two-sided. All efficacy endpoints will be analyzed on the intent-to-treat (ITT) population during the cohort study (every year). The ITT population will include all subjects who were initiated under treatment (at least one prescription of HCV treatment).

Analyses will be performed using STATA, version 13 (StataCorp, College Station, Texas).

VI. Tools

Demographic and clinical data is currently collected via case reporting forms (CRFs) and laboratory forms. Data is collected on: individual baseline information, clinical evaluation information, laboratory results and treatment information. The CRFs are presented in Appendix 1-4. (All forms are currently being used for recording clinical management of new HCV patients entering treatment). De-identified data is entered in to an electronic database and used for reporting and monitoring and evaluation of HCV treatment activities.

Study participants will be linked through unique study numbers assigned to study participants. Personal identifier information will be recorded only on CRFs, and will be kept separately to maintain confidentiality.

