A trained clinician/counselor will administer the information sheet verbally, encouraging questions. When it is deemed the subject has a good understanding they will be asked to sign the consent form. The subject will sign the informed consent document prior to any study-related analysis of their data. Subjects will be given the opportunity to discuss the study with their surrogates or think about it prior to agreeing to participate. The participant, if functionally illiterate, may sign the consent by marking with a thumbprint on the signature line. The presence of a witness who will also have to sign the document will also be encouraged. The subject may withdraw consent at any time throughout the course of the study. A copy of the signed informed consent document will be given to subjects for their records. The rights and welfare of the subjects will be protected by emphasizing to them that the quality of their clinical care will not be adversely affected if they decline to participate in this study.

XII. Timelines

The study has an estimated start date of December 2016, and with the end of inclusions being December 2018. Table 2 provides a breakdown of the study timetable for the Manipur sites.

Table 4: Study Timeframe

Activities	Time
Protocol development and submission to MSF Ethical Committee	Jan 2016-April 2017-
National Protocol developments and submission to NACO	April 2016 – Nov 2016
Field preparation and pilot study	Nov-Dec 2016
Recruitment	May 2017 to May 2019
Follow-up patients	May2017 toAug 2019
Field data management	May 2017 to Aug 2019
Regular Data analysis and Monitoring_ interim reports	May 2016 to Aug 2019
Final report (including outcomes)	Dec 2019
External communication	Jan 2020

7. FACILITIES IN TERMS OF EQUIPMENT, ECT, AVAILABLE AT THE INSTITUTION / ORGANISATION FOR THE PROPOSED INVESTIGATION

The treatment activities on which this observational study will be performed are on-going programmatic activities within the MSF clinics located in Churachandpur, Chakpikarong and Moreh. Within these locations MSF in partnership with NACO, operate as outpatient facility with associated on-site laboratory capacity. Each of these laboratories is capable of performing routine biochemistry, haematology, CD4 counts, serological testing HIV / HCV / HBV / Syphilis and Microscopy. Each also has a GeneXpert machine. In addition a mobile Fibroscan machine is present and can be moved between these sites.

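### Table 4 closes follow-up about 13 to 17 weeks after recruitment ends, but SVR12 falls 24 or 36 weeks after treatment start, so late starters cannot reach the primary endpoint

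*Protocol*

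**What the plan says.** Section 6.XII gives two recruitment windows. Table 4 has recruitment "May 2017 to May 2019". The text above it starts in December 2016, "with the end of inclusions being December 2018". Table 4 gives patient follow-up as "May2017 toAug 2019", closes field data management in the same month, and dates the final report with outcomes December 2019.

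Section 6.VIII fixes the endpoint: "The endpoint will be plasma HCV-RNA response at week 12 after end of treatment (EoT"). Its denominator is everyone who started HCV treatment, whatever the regimen. Failure is a detectable viral load at that time point, death, loss to follow-up, a medical exit or a transfer out. Loss to follow-up can be declared only two months after a planned appointment without contact.

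Section 6.I says that each patient is followed until SVR12 or one of the exit events, with no calendar limit. Tables 2 and 3 list regimens of 12 and 24 weeks. Section 6.V states: "All efficacy endpoints will be analyzed on the intent-to-treat (ITT) population during the cohort study (every year"). A single HCV prescription is enough to enter that population.

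**The concern.** The protocol itself fixes the calendar, the endpoint time, the denominator and the analysis frequency, and these do not fit together. A patient who starts treatment near the end of the Table 4 recruitment window will still be on treatment, or within 12 weeks of finishing it, when follow-up and data management close. That patient belongs to the primary denominator but is neither a success nor a failure under section 6.VIII. The form that records the end of follow-up (CRF2, item 290) has no code for study closure either.

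The analyst must then improvise: drop these patients, count them as not cured, or wait for results beyond the planned close. Each choice gives a different primary proportion. The truncation also falls harder on 24-week regimens, so it can distort SVR12 by regimen and genotype as well as the overall figure. The same question arises at every yearly analysis, with a larger share of patients pending.

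**Working it through.** **Inputs.** From Table 4: recruitment to May 2019, follow-up to August 2019, report in December 2019. From the text of 6.XII: inclusion to December 2018. From Tables 2 and 3: treatment of 12 or 24 weeks. From 6.VIII: SVR12 at 12 weeks after the end of treatment. The document gives months only; I take August to end on the 31st, which favours the plan. The plan gives no figure for endpoint maturity. Its expected sample size does reproduce (1600 × 0.27 × 0.80 = 345.6, stated as 345), but that is a count of patients included, not of patients treated.

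**Time needed from first dose.** 12 + 12 = 24 weeks, or 24 + 12 = 36 weeks.

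**Time available under Table 4.** 31 May to 31 August 2019 is 92 days, or 13.1 weeks. From 1 May it is 122 days, or 17.4 weeks. The shortfall is:
- 12-week regimens: 24 − 17.4 = 6.6 weeks to 24 − 13.1 = 10.9 weeks
- 24-week regimens: 36 − 17.4 = 18.6 weeks to 36 − 13.1 = 22.9 weeks

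**Last start that can be observed by 31 August 2019.** Subtracting 168 days gives 16 March 2019 (12-week). Subtracting 252 days gives 22 December 2018 (24-week).

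**Share of starters affected.** Assume uniform starts from 1 May 2017 to 31 May 2019 (760 days) and no wait from inclusion to treatment.
- All on 12-week regimens: 16 March to 31 May is 76 days; 76/760 = 10.0%
- All on 24-week regimens: 22 December to 31 May is 160 days; 160/760 = 21.1% (upper bound)

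**Under the text's date.** From 31 December 2018 to 31 August 2019 is 243 days, or 34.7 weeks; from 1 December it is 39.0 weeks. A prompt 12-week starter fits, with 243 − 168 = 75 days (10.7 weeks) to spare. A prompt 24-week starter fits unless treatment begins after 22 December, so the worst case is 252 − 243 = 9 days short. A patient included on 31 December who waits more than 10.7 weeks for treatment no longer fits on any listed regimen. The protocol expects such waits: inclusion does not depend on treatment eligibility, untreated patients may be treated later, CRF2 has a waiting-list option, and eligibility is reassessed yearly.

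**Against the report date.** For a start on 31 May 2019, SVR12 falls on 15 November 2019 (12-week) or 7 February 2020 (24-week). For 24-week regimens, SVR12 falls after 31 December 2019 if treatment starts after 23 April 2019. That is 38/760 = 5.0% of the window.

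**Yearly analyses.** With uniform starts, the share not yet at SVR12 after one year is 24/52 = 46% if all regimens last 12 weeks and 36/52 = 69% if all last 24 weeks (upper bound). After two years it is 24/104 = 23% and 36/104 = 35%.

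**The case against.** The strongest reply is that the final-analysis gap depends on which of two conflicting dates applies. With inclusion ending in December 2018, prompt starters almost all fit. That stands, but it helps only if inclusion and treatment start coincide, and Table 4 still prints the unworkable window.

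Secondly, the shares are illustrations. All three non-cirrhotic genotype rows list a 12-week regimen, so a cohort entirely on 24 weeks is not what the tables describe. Patients come from a standing clinic population with serology since 2012, so early enrolment could shrink the late tail; the waiting list could lengthen it. This also stands: the direction is unknown.

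Thirdly, a reader might infer that the reported cure rate will be biased down. With an assumed true SVR12 of 95%, all patients on 24 weeks and a 12-week wait, 32% would be pending and the rate would read 0.95 × (1 − 0.321) = 65%. The document does not support that. Being short of the week-12 visit is not among its failure events, so nothing tells the analyst to count pending patients as failures. The defect is an undefined status, not a known bias.

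Finally, a maturity rule for interim tables is often left to the SAP, which is not at hand, and the protocol ties no decision to the yearly results. That lowers the weight of the yearly part. It does not remove it, because section 6.V itself sets yearly efficacy analysis on everyone who has started treatment.

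**Conclusion.** The point holds. On Table 4's dates no listed regimen allows a patient who starts treatment in May 2019 to reach SVR12 before follow-up closes, and the commitment in section 6.I to follow patients until SVR12 cannot be met for late starters. This rests on the protocol's own dates and durations alone.

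The size is less certain: about 10% to 21% of starters on uniform, immediate starts, where 21% requires every patient to be on 24 weeks. The true share depends on accrual, regimen mix and waiting time, none of which is given. The text's December 2018 date reduces the gap to at most 9 days for prompt starters but leaves it open for delayed ones.

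A reader might also infer that the December 2019 report precedes all late SVR12 results. It does not: the last 12-week result is due on 15 November 2019, and only 24-week regimens started after about 23 April 2019 fall beyond the report. The yearly analyses share the undefined status of pending patients under either recruitment date.

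**What to change.** 1. Use one recruitment window in the text of section 6.XII and in Table 4.
2. Run follow-up and field data management at least until the SVR12 visit of the last patient counted in the primary analysis can be observed: planned duration plus 12 weeks, with an allowance for the two-month loss-to-follow-up rule. For a start on 31 May 2019 this means 15 November 2019 plus two months (15 January 2020) for 12-week regimens, or 7 February 2020 plus two months (7 April 2020) for 24-week regimens. Move the final report accordingly. Alternatively, keep the close and set a last treatment-start date for the primary analysis.
3. State in section 6.V that each yearly and final SVR12 proportion uses all initiated patients whose planned SVR12 date, plus that allowance, falls on or before the data cut, and that the protocol's own failure definitions apply within that set.

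The cost is an amendment to the timetable and a short addition to section 6.V. No extra visits are needed, since the viral load 12 weeks after treatment is already in the laboratory schedule. The price is a later final report or, if a last start date is chosen, a set somewhat smaller than the stated denominator of all who initiated treatment. The amendment should say openly that the denominator is narrowed.
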